#### **9.6.2.5.2 Stratified Analysis**

None

#### **9.6.2.5.3 Other Sensitivity Analysis**

Additional sensitivity analyses are described below:

1. Analyses varying exposure cutpoints and definition of exposure:

For all primary and secondary outcomes, additional subgroups based on timing of exposure will also be assessed, such as women exposed to erenumab during the following time periods: 1) in the 12 or 16 weeks (for the 70mg and 140 mg doses, respectively) prior to or during the pregnancy; 2) at any point during the pregnancy; 3) and in each trimester. The number and timing of erenumab-aooe doses will also be assessed for each outcome.

2. Analyses varying enrollment criteria

Women who have continuous enrollment in the health plan for only 180 days prior to the LMP will also be assessed to allow for more women to be included. Sensitivity analyses relating to missed outcomes arising from non-linkage of the infant data, or infant disenrollment from the health plan will also be conducted. We will evaluate non-linkage at 30 days, at 60 days, and at 90 days to evaluate potential attrition bias as a result of disenrollment. These analyses will be further detailed in the SAP.

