###### *Secondary:*

Pregnancies ending in spontaneous abortion, defined as spontaneous losses before 20 weeks of gestation, and identified using ICD-10-CM diagnosis and procedure codes.

Pregnancies ending in stillbirth, defined as *in utero* fetal deaths 20 weeks of gestation and after, and identified using ICD-10-CM diagnosis and procedure codes.

Small-for-gestational age in live-born infants, defined as birth weight 10th percentile, and identified using ICD-10-CM diagnosis codes.

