are classified as an FDA category C drug. Data from a prospective pregnancy registry observed birth defects in 4.2% (95% confidence interval (CI) 2.6%-6.5%) of infants born to women using sumatriptan during pregnancy (Ephross and Sinclair 2014), which is consistent with general population birth defect rates. Preventive medications that may be used during pregnancy include memantine and beta blockers, such as propranolol (Robbins 2018). Beta-blockers are generally thought to be safe and are commonly used to treat hypertension in pregnant women; however, they may be associated with intrauterine growth restriction (Robbins 2018). Topiramate and valproic acid should be avoided during pregnancy due to their teratogenic effects (Robbins 2018; Hernandez-Diaz et al, 2012).

Erenumab-aooe is a human monoclonal antibody (mAb) that inhibits the receptor for calcitonin gene related peptide (CGRP) and is indicated for the preventive treatment of migraine. Although clinical trials have demonstrated erenumab has a favorable risk benefit profile, there are no adequate and well-controlled studies on the use of erenumab-aooe in pregnant women. In animal reproduction studies, there were no effects on pregnancy or neonatal/infant development when monkeys were administered erenumab-aooe SC from organogenesis through parturition at exposures up to 16-fold the exposure at the maximum recommended human dose of 140 mg monthly.

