### **9.3 Variables**

#### **9.3.1 Exposure Assessment**

Pregnant women who have pharmacy claims for erenumab-aooe (identified using NDC codes) in the 112 days prior to the LMP date (to allow for the half-life of erenumab) or during the pregnancy will be considered exposed to erenumab-aooe.

Exposure to erenumab-aooe will be categorized by dose (70 mg versus 140 mg), by length of exposure, and by timing in relation to trimester of pregnancy: before the last menstrual period (LMP, in the 112 days prior to the EDC, this is the exposure window of interest for major malformations), during the first trimester (from the LMP to 90 days after the LMP), during the second trimester (from day 91 after the LMP to day 180 after the LMP), and during the third trimester (from day 181 after the LMP to the end of pregnancy) (see [Section 9.3.1.1](#) for definitions of LMP).

For the comparator cohorts, comparator group A will include pregnant women with migraine who do not have pharmacy claims for erenumab-aooe in the 112 days prior to the LMP but do have evidence of the use of other preventive migraine medications. Comparator group B will include pregnant women with migraine who do not have pharmacy claims for erenumab-aooe or other anti-CGRP medications 112 days prior to the LMP date or during pregnancy

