### **9.6.2.5 Sensitivity Analysis**

#### **9.6.2.5.1 Subgroup Analysis**

Subgroups that will be explored if there is sufficient sample size include maternal age group at LMP (16-17 years, 18-40 years, 41-44 years), calendar year at LMP, comorbidities or medication use at baseline, concomitant medication use during pregnancy, dose of erenumab-aooe taken (70 or 140 mg), and patients who have migraine with aura or chronic migraine.

In addition to assessing outcomes in pregnant women exposed to erenumab-aooe before or during pregnancy and those not exposed to erenumab-aooe before or during pregnancy, we will also explore proportions of each of the outcomes in subgroups of the unexposed cohort, including migraine patients exposed to other CGRPs, migraine patients exposed to erenumab more than 112 days prior to the estimated date of conception and not during the pregnancy, migraine patients exposed to other preventive migraine medications, and migraine patients exposed to known teratogens in the one month prior to or during pregnancy. Also, outcomes will be described in migraine patients with claims for acute medication during the pregnancy.

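### Trimester, dose-count and duration categories for spontaneous abortion and stillbirth are cut off by the end of pregnancy, so these sensitivity results mislead even if the drug has no effect

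*Protocol*

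**What the plan says.** Section 9.6.2.5.3, item 1, sets the scope: "For all primary and secondary outcomes, additional subgroups based on timing of exposure will also be assessed". The listed periods include any point in pregnancy and each trimester. The item ends: "The number and timing of erenumab-aooe doses will also be assessed for each outcome".

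Section 9.3.1 also classifies exposure "by length of exposure, and by timing in relation to trimester of pregnancy". The second-trimester window covers days 91 to 180. The last window is "during the third trimester (from day 181 after the LMP to the end of pregnancy". The Abstract gives spontaneous abortion as "defined as spontaneous losses before 20 weeks of gestation".

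Section 9.6.2.5.1 adds a subgroup defined by events during pregnancy: "outcomes will be described in migraine patients with claims for acute medication during the pregnancy".

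Under Sections 9.6.2.4.1 and 9.6.2.4.2, the loss outcomes are analysed as proportions. If numbers allow, odds ratios weighted on baseline confounders follow. The protocol mentions no landmark, time-varying exposure or risk set at the start of each trimester.

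**The concern.** A woman can be in the second- or third-trimester group only if her pregnancy lasts that long, and she can collect many doses during pregnancy only if it does not end early. For the two loss outcomes, the exposure category is therefore partly a result of the outcome. The same holds for length of exposure and for subgroups defined by medication claims during pregnancy.

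These are the results a reader would turn to for timing or amount of exposure in a pregnancy safety study. Later exposure would appear to go with very little loss under no effect, and a real harm could be hidden in the same tables.

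The planned safeguards do not reach the problem. Weights on baseline covariates cannot correct truncation that happens after baseline. The quantitative bias analyses in Section 9.6.2.5.3 name confounding and misclassification only. Section 9.8.1 does not list a time-related bias, although the checklist in Appendix A ticks that item and points to Section 9.8.1.1.

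**Working it through.** The plan states no figure for this bias, so there is none to reproduce. The first two steps use the protocol's own definitions. The rest use assumptions, which are stated.

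**1. Windows.** 20 weeks × 7 = day 140. The second trimester starts on day 91 (91/7 = 13 weeks) and the third on day 181. Since 140 < 181, spontaneous abortion among third-trimester-exposed women is exactly 0%. Table 1 gives a maximum of 10.0 weeks (day 70) for spontaneous abortion under Method 1, the type of approach Section 9.3.4 proposes. Where that fixed assignment is used, the second-trimester figure is also 0%, because 70 < 91. Method 1 places stillbirth at 28.0 weeks at most (day 196). Such a stillbirth leaves 196 − 181 = 15 days for a third-trimester fill, against 273 − 181 = 92 days for a birth at an assumed 39 weeks.

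**2. Possible doses.** Section 7.1 refers to a "maximum recommended human dose of 140 mg monthly"; I take one fill per 28 days. Possible fills from the LMP = floor(days/28) + 1:
- last day before day 140: floor(139/28) + 1 = 5
- mean age at spontaneous abortion, 9.9 weeks: floor(69.3/28) + 1 = 3
- mean age at stillbirth, 27.8 weeks: floor(194.6/28) + 1 = 7
- about 39.5 weeks: floor(276.5/28) + 1 = 10

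**3. Hand check for day 91.** Assume a true risk of 15% and gestational age at loss normal with mean 9.9 weeks (Table 1, Method 1) and SD 3 (assumed). The share of losses after week 13 is 1 − Φ((13 − 9.9)/3) = 0.151. Risk among pregnancies ongoing at day 91 = 0.15 × 0.151 / (0.85 + 0.15 × 0.151) = 2.6%. For 10% and 20% it is 1.6% and 3.6%. Second-trimester-exposed women come out lower still, because a loss soon after day 91 leaves little time for a fill.

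**4. Simulation with no drug effect.** 500,000 pregnancies per scenario; spontaneous abortion timed as in step 3; stillbirth 0.6%, mean 27.8 weeks, SD 4; live birth mean 39 weeks, SD 1.8. Fills after the LMP ignore the outcome and end with the pregnancy. The risks and SDs are assumptions. At a 15% true risk of spontaneous abortion:

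| Fill pattern | 1 dose | 2 | 3 | ≥4 | Odds ratio, ≥3 vs 1-2 |
|---|---|---|---|---|---|
| 60% chance of a fill each month | 96.7% | 81.1% | 28.5% | 0.3% | 0.003 |
| 40% chance of stopping per month | 16.9% | 20.6% | 15.7% | 1.8% | 0.38 |
| 20% chance of stopping per month | 20.0% | 30.9% | 26.5% | 1.8% | 0.26 |

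By trimester of exposure, spontaneous abortion is 13.9-15.0% (first), 0.6-1.1% (second) and 0% (third). Over assumed risks of 10-20%, the second-trimester figure is 0.4-1.5%. Further null runs on other assumptions gave 1.7-1.8% at 15%, and 1.1-2.4% over 10-20%.

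Stillbirth among third-trimester-exposed women is 0.24-0.39% against 0.6%. By dose count its odds ratio (≥3 vs 1-2) runs from 0.75 to 1.46, with no consistent direction.

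**5. Sensitivity of the dose-count pattern.** Two further null runs at 15%:
- If use stops at pregnancy recognition (assumed weeks 4-8), risk is 15.9% with one dose after the LMP and 14.2% with two, so the artefact nearly vanishes.
- If doses before the LMP are counted too, with random stopping, risk is about 15% for 1-4 doses, 24-38% for 5-7, and 0% only from 10 doses.

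**6. Does the repair work?** Count doses up to day 56 among pregnancies still ongoing, then compare later spontaneous abortion. For 0, 1 and 2 doses the risk is 11.6%, 11.5% and 11.5% with steady fills, and 11.6%, 11.5% and 11.4% with 40% monthly stopping. The artefact is gone.

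**The case against.** The strongest reply is that the protocol fixes little. The subgroups are sensitivity analyses introduced as examples, no trend test or contrast between dose strata is stated, and risk sets are commonly left to a statistical analysis plan. That is fair about detail. But the protocol itself assigns the trimester and dose-count categories to every outcome, including a cell that cannot contain an event. Tabulating proportions exactly as described gives the misleading result without any formal contrast.

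Second, Section 9.2.3 matches cohorts 1:4 on LMP date and gestational age. If that means gestational age at exposure, a comparison of an exposure-window subgroup with its own matches would be largely protected. The text does not say so, and the matching is between cohorts, so it does nothing for comparisons across strata of the exposed.

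Third, a zero for spontaneous abortion in third-trimester users is visibly definitional. That is true of that cell, but less so of a 1-2% second-trimester figure or a low risk at four or more doses.

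Fourth, a reader might infer that more doses will always look protective against loss. The results do not support that. Risk rises from one to two doses in two of the three fill patterns, can rise before it falls when doses before the LMP count, and barely moves if women stop early. The stillbirth direction by dose count is unreliable. This objection stands and limits the point.

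**Conclusion.** The point holds for the two loss outcomes only. The 0% for spontaneous abortion with third-trimester exposure follows from the definitions alone. The near-zero second-trimester figure (about 1-2% against an assumed 15%) and the understated stillbirth risk with third-trimester exposure rest on assumed risks, timing and fill patterns, but their direction was the same in every scenario run. Dose-count results are distorted in a way that cannot be signed across the whole range. Results by length of exposure share the mechanism; no separate size was computed for them or for the medication-claim subgroups.

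A reader might also infer that malformations, small-for-gestational-age or the main cohort comparison are biased by these categories. The documents do not support that. Both infant outcomes are assessed in live births, no bias was shown for them, and the primary comparison does not rest on these strata. A special dose-counting cut-off for malformations is not needed on this ground.

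The change is worth making, but the study's primary conclusion does not depend on it.

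**What to change.** For spontaneous abortion and stillbirth, amend Section 9.6.2.5.3 (and the use made of the Section 9.3.1 categories) as follows:

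- Among pregnancies still ongoing at a fixed gestational day, classify number of doses, length of exposure and trimester exposure using claims up to that day only, and compare later loss. Days 28, 56 and 84 would serve for spontaneous abortion and day 140 for stillbirth. Alternatively, treat exposure as time-varying; exposure after the last landmark, such as third-trimester exposure for stillbirth, needs this form.
- Drop third-trimester exposure for spontaneous abortion.
- Apply the same rule to subgroups defined by medication claims during pregnancy (Section 9.6.2.5.1) when the outcome is a loss.
- State whether doses in the 112 days before the LMP enter the dose count.

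The cost is a few sentences and modest programming. Later landmarks contain fewer pregnancies, and losses before the landmark leave the analysis. In the 15% scenario with day 56, solving (0.15 − x)/(1 − x) = 0.115 gives x = 0.035/0.885 = 0.04, so about 4 of the 15 percentage points are lost. That is why more than one landmark is advisable.

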### 3. Quantitative bias analyses

Quantitative bias analyses will be explored to assess the impact of sources of error such as residual confounding, and misclassification of exposures, covariates, or outcomes.

### 4. Other sensitivity analyses

We will also conduct sensitivity analyses limited to just the first pregnancy, and only among patients with no prior history of adverse pregnancy outcomes.

Patient characteristics and primary and secondary endpoints will also be described in any patients receiving erenumab who do not have a diagnosis for migraine in the chance of off-label use.

Analyses of major congenital malformations will also be conducted in all live born infants (not restricting to those with at least 90 days of follow-up) and limited to infants with at least a year of follow-up/enrollment after birth.

### **9.6.3 Analysis of Safety Endpoint(s)/Outcome(s)**

This is a study to assess the safety of erenumab-aooe on maternal and fetal outcomes when mothers are exposed to erenumab-aooe during pregnancy. Safety outcomes include major congenital malformations in infants, pregnancies ending in spontaneous abortion or stillbirth, and infants who are small-for-gestational age. The proportion of live-born infants who have major congenital malformations or are small-for gestational age, and the proportion of pregnancies ending in spontaneous abortion or stillbirth will be estimated in an erenumab-aooe-exposed cohort and in an unexposed cohort of pregnant women with migraine.

### **9.7 Quality Control**

For the MarketScan CCE database analyses, the quality assurance process involves review at each step in analytic file build. Reviews of all study programming are performed by a second analytic programmer, including the patient selection and

extraction process, variable definitions, each individual analysis, and table or figure construction.

To help ensure the highest level of quality on every project, HealthCore has established several layers of quality assurance throughout the project lifecycle.

**Role Based Control Checks:** each member of the team is responsible for performing thorough quality control checks on their work; in addition, the Principal Investigator and Research Project Manager are accountable for quality of all deliverables.

**Quality Check Points:** centralized “checkpoints” have been implemented during the data management cycle to help ensure accurate translation of programming requests.

**Quality Assurance Standards:** standard review procedures have been developed and are applied throughout the project lifecycle.

**Automation:** HealthCore has developed standard definitions of many variables and disease states and developed programs to apply these standards as needed on projects. These standards help ensure consistency, repeatability and accuracy for each project.

HealthCore documents study progress, and scientific and quality review of all study activities and deliverables (eg, protocol, data management, data analysis, reports, manuscripts, etc.) in an Action, Decision, Issue, Notification (ADIN) log and in a Quality Control (QC) log. The ADIN log provides documentation of study progress, action items, issues/issue resolution, and notifications, and is updated weekly during internal project team meetings. In addition, the QC Log documents the quality control measures performed for each study activity during the conduct of the study.

All programming required for study database extraction and creation of the analytic datasets from the HIRD will be performed in accordance with HealthCore Programming Standards. The HealthCore Programming Standards are a set of documents describing data extraction methods that are referenced in HealthCore Standard Operating Procedures (SOPs) and provide a guideline for basic, frequently used terms and definitions and respective coding information to maintain operational consistency. Data validation will occur throughout the data management and analysis process. Data quality checks include, but are not limited to, programming checks by an individual who is not the main programmer for the study, internal dataset consistency, and checks to ensure that protocol criteria were met.

## **9.8 Limitations of the Research Methods**

There are several methodological issues associated with the use of administrative claims databases when investigating outcomes of drug exposure during pregnancy. In particular, key challenges relate to the identification of pregnancy episodes, determination of gestational age, the linkage of mothers and infants, and ascertainment of exposures and outcomes; thus, careful interpretation of results is needed in light of study and data limitations.

### **9.8.1 Internal Validity of Study Design**

#### **9.8.1.1 Measurement Error(s)/Misclassification(s)**

The algorithm used for identification of pregnancy episodes and outcomes for pregnancies that end in live births is very robust (99% agreement between algorithm and chart review). However, ascertainment of LMP and gestational age for pregnancies ending in spontaneous abortion or stillbirth is challenging. We will use a previously published method, such as Hornbrook et. Al. to estimate gestational age and LMP.

As with any observational study conducted within the context of an insurance claims database, drug exposure and timing of exposure is never entirely certain. Although there is evidence in the claims of patients receiving a prescription dispensing at an outpatient pharmacy, we are unable to verify that patients actually used the medication.

Conversely, pregnant patients may take pills during pregnancy that were obtained from a prescription written and dispensed prior to the conception date. In addition, the prescription database lacks information on non-reimbursable (over-the-counter) analgesics, medication dispensed during hospital admissions, or obtained from the doctor's office as samples.

The completeness and/or sensitivity of some of the covariates of interest, such as body mass index, alcohol, tobacco and substance abuse, and previous history of congenital malformations, may be low, and residual confounding due to these characteristics may still be present.

#### **9.8.1.2 Selection Bias**

The generation of mother-infant pairs is dependent on the infant being covered under the same insurer as the mother, and our mother-infant linkage algorithm could only link about 77% of live-born infants to their mothers (based on a completed exploratory analyses). The matched mothers were older (mean age 32.1 years) than the unmatched mothers (mean age 27.2 years), likely because younger mothers are

covered by their parents' health insurance. Other than age, the matched mothers were comparable to the unmatched mothers with regard to geographic region, gestational age, and occurrence of pharmacy dispensation during pregnancy.

The migraine case identification algorithm has not been validated in the MarketScan CCE database. Previously reported literature ([Kolodner et al, 2004](#)) and internal validation work in the Pharmetrics and Decision Resources Group claims linked with electronic health record databases showed that the algorithm has very high specificity but low sensitivity. Thus, it is possible that some migraine patients will be misclassified as non-migraine patients and will be excluded from this study. However, use of erenumab-aooe will not likely be missed as migraine diagnosis codes should appear in claims records due to its insurance coverage requirements.

Women will be followed through their pregnancy, and their live-born infants will be followed for one year after birth, or until the end of enrollment in the database. It is possible that we may miss outcomes if enrollment ends prior to the outcome. Differential loss to follow-up is a type of selection bias that poses a potential threat to the internal validity of any study. Loss to follow-up can be broadly conceptualized as any termination of treatment prior to the administrative end of the study, including, but not limited to, drop-out as a result of change in health plan, drop-out due to illness/frailty. For our study, we consider only health plan disenrollment. If all disenrollment occurred at random there would be loss in precision, but no increase in bias of the effect estimate. In most studies using claims data, we assume that health plan disenrollment does not occur at random. We will use sensitivity analysis to evaluate the potential impact of attrition bias.

#### **9.8.1.3 Confounding**

Confounding by baseline covariates will be addressed with the use of inverse probability of treatment weights. We rely on subject matter knowledge to include candidate confounding variables in our analyses, but residual confounding may exist as a result of unmeasured or incomplete confounders (eg, obesity, use of alcohol, smoking, illicit drug use) or unknown confounders. We will include even weak confounders in the final analysis, sacrificing precision of our final effect estimates by guarding against the potential bias that might be introduced by omission of the confounder. The approach to address unmeasured confounders is addressed in [section 9.8.4](#).

